30.04.2023

Evaluation of the Effects of A-Prf and Oral Dexamethasone Use on Postoperative Complications in Third Molar Tooth Extraction

Study Protocol

This study was conducted on 30 patients who were referred to XXX Oral and Maxillofacial Surgery Clinic and were indicated for extraction of impacted third molars. After clinical and radiographic evaluations of all patients, bilateral similarly positioned lower wisdom teeth with full mucosal retention were included.

The tooth extraction on one side of each patient constituted a study group and the other tooth extraction constituted the control group. In Group 1, A-PRF was placed in the patients' tooth extraction sockets and the flap was closed primarily using 3/0 silk suture. The patients were formed into Group 2 so that the other tooth would be extracted 5 weeks later. In Group 2, primary closure was achieved with 3/0 silk suture without placing any biomaterial in the extraction socket, and after the procedure, the patient was prescribed oral dexamethasone (Dekort 4 mg tablet, S:3*1 DEVA brand) with the statement that it would be used for 3 days.

Surgical Technique and Application

Before the operation, the patients included in the study had their radiological orthopantomography taken and their clinical examinations were performed.

The impacted wisdom teeth of the patients were extracted under local anesthesia after determining which tooth would be extracted first and which group it would be included in a random manner. The patient was administered local anesthesia with 1/100,000 epinephrine containing Ultracain D-S Forte® (Sanofi Aventis, Istanbul-Turkey) and after mandibular, lingual and buccal anesthesia, an envelope incision was made and the flap was lifted. Depending on the position of the tooth, the tooth was removed by separating or dividing it when necessary.

Before the operation where the surgical area where A-PRF would be applied was located, 1 tube, 10 cc (Ayset tube, Ayset Tibbi Ürünler San. A.Ş., Adana/Türkiye) of blood was taken by the assistant personnel. Blood collection was performed via the peripheral antecubital vein by selecting the appropriate intracatheter for the patient's vascular structure. Care was taken to ensure that the patient was in a comfortable position during blood collection. The collected blood was centrifuged for 14 minutes at 1500 rpm using a centrifuge device (Intra-Lock Intra-Spin L-Prf Device, Intra-Lock International, Inc., FL, USA). The A-PRF obtained at the end of centrifugation was placed in the embedded wisdom tooth extraction cavity and the region was closed primarily.

All patients were prescribed amoxicillin 1000 mg (Largopen 1000 mg, 3*1), ibuprofen 600 mg (Brufen 600 mg, 2*1), benzydamine hcl + chlorhexidine gluconate mouthwash (Chloroben 200 ml mouthwash, 3*1) after the operation. They were asked to use the antibiotic and mouthwash as recommended and to take painkillers when needed. The sutures were removed 1 week later.

The VAS scale was used for the patients' pain assessments. Patients were instructed on how and at what times to fill out the scale, and were asked to fill in the scores from 0 to 10 (0, no pain; 10, unbearable pain) at hours 3, 6, 9, 12, and 24 and days 2, 3, 4, 5, 6, 7, 14, and 30. In order to evaluate the patients' analgesic use, patients were asked to note their additional analgesic use on the forms given to them.

For the patients' edema evaluations, the angulus-tragus, angulus-lateral canthus, angulus-nasal wing, angulus-labial commissure, angulus-pogonion face measurements were made before the operation, on the 2nd day after the operation, on the 7th day, 14th day, and 30th day after the operation. For the patients' trismus evaluations, the maximum mouth opening and the distance between the incisal edges of the central teeth in the most open position of the mouth were measured before the operation, on the 2nd day after the operation, on the 7th day, 14th day, 14th day, and 30th day after the operation.

Statistical Analyses

While evaluating the findings obtained in the study, NCSS (Number Cruncher Statistical System) 2020 Statistical Software (NCSS LLC, Kaysville, Utah, USA) program was used for statistical analysis. While evaluating the study data, quantitative variables were shown with mean, standard deviation, median, min and max values, and qualitative variables were shown with descriptive statistical methods such as frequency and percentage. Shapiro Wilks test and Box Plot graphics were used to evaluate the conformity of the data to normal distribution. Wilcoxon Signed Ranks Test was used in intra-group comparisons of parameters that did not show normal distribution, and Dunn was used to determine the group causing the difference. The results were evaluated at a confidence interval of 95%, and significance was at the level of p<0.05.

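### Both sides are actively treated, so the two-sided design can estimate only A-PRF minus dexamethasone; the plan should make that paired difference its treatment-effect result and treat intra-group changes as descriptive.

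*Combined protocol and SAP*

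**What the plan says.** The title is "Evaluation of the Effects of A-Prf and Oral Dexamethasone Use on Postoperative Complications in Third Molar Tooth Extraction". The plan has no separate objective, hypothesis or estimand.

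The Study Protocol section describes a split-mouth design: "This study was conducted on 30 patients", with two extractions each. On the roles of the two sides it says: "The tooth extraction on one side of each patient constituted a study group and the other tooth extraction constituted the control group".

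The treatments are:

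- Group 1: "In Group 1, A-PRF was placed in the patients' tooth extraction sockets and the flap was closed primarily using 3/0 silk suture".
- Group 2: "In Group 2, primary closure was achieved with 3/0 silk suture without placing any biomaterial in the extraction socket", and then "the patient was prescribed oral dexamethasone (Dekort 4 mg tablet, S:3*1 DEVA brand) with the statement that it would be used for 3 days".

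Under Surgical Technique and Application, all patients receive the same antibiotic, ibuprofen and mouthwash, so these do not distinguish the sides. That section also sets the outcomes: VAS pain at 13 postoperative times, and five facial distances and mouth opening before surgery and at visits up to day 30.

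Under Statistical Analyses, the test is introduced this way: "Wilcoxon Signed Ranks Test was used in intra-group comparisons of parameters that did not show normal distribution". Dunn is then named for locating the group responsible for a difference. No sentence says which contrast measures the effect of treatment.

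**The concern.** The sides differ in two things at once: one has A-PRF without dexamethasone, the other dexamethasone without A-PRF. A side labelled as control is usually read as showing what happens without the study treatment. Here it carries a different active treatment. The plan does not say that its answer is the difference between the two, and the signed-rank test is attached to a comparison that, read in the ordinary sense, looks within one group over time.

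Two misreadings are then at risk:

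- Recovery after surgery, which is expected over 30 days in any case, could be credited to each treatment because the intra-group tests are significant.
- A non-significant side-to-side result could be read as A-PRF having no effect, when it is equally compatible with both treatments working to the same degree.

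**Working it through.** The plan gives no sample-size, power, effect-size or SD figure, so there is no figure of its own to reproduce. The check has three parts.

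**1. What two sides per patient can estimate.** Let p be a patient's level without either treatment, a the A-PRF effect and d the dexamethasone effect, each against no treatment.

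- A-PRF side: p + a
- Dexamethasone side: p + d
- Difference: (p + a) − (p + d) = a − d

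Replacing p, a and d by p + c, a − c and d − c leaves both expected values unchanged for any c. So a and d cannot be recovered separately, but a − d can. For example, true effects of (−2, −2) and (0, 0) VAS points both give a difference of 0. A rank check on the full model with 30 patient effects gives the same answer: a − d is estimable, and a and d alone are not. They become estimable only if an untreated condition is added.

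**2. Dependence on order.** Add an effect π for the second extraction.

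- A-PRF first: difference = a − d − π
- Dexamethasone first: difference = a − d + π

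If order was randomised, both kinds of patient exist and the mean of the two order-specific differences is a − d. If Group 2 was always second, every patient gives a − d − π, and a − d cannot be separated from π. The Study Protocol section places the Group 2 extraction five weeks after the other. Surgical Technique and Application says that order and group were determined randomly. These cannot both be taken at face value.

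**3. What intra-group tests over time would show if neither treatment worked.**

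Inputs: n = 30 (Study Protocol) and the 0.05 level (Statistical Analyses), taken as two-sided because sidedness is not stated. Assumed: mean natural recovery δ between two visits, in SDs of the within-patient change. A paired t-test stands in for the signed-rank test.

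The critical value is t(0.975, 29) = 2.045. The probability of significance is P(|T| > 2.045), where T is noncentral t with 29 df and noncentrality δ√30.

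| δ (SD, assumed) | δ√30 | Probability of p<0.05 in each group |
|---|---|---|
| 0.3 | 1.64 | 0.36 |
| 0.5 | 2.74 | 0.75 |
| 0.7 | 3.83 | 0.96 |
| 1.0 | 5.48 | 0.9996 |

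Simulating the signed-rank test on normal data gives slightly lower values: about 0.73 to 0.74 at 0.5 SD and above 0.99 at 1 SD.

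**Precision of the contrast that can be estimated.** The half-width of the 95% CI for the mean paired difference is 2.045/√30 = 0.373 SD of that difference. A non-significant result therefore leaves a range of differences open and does not show equality.

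**The case against.** The strongest reply is that an active-controlled comparison is a legitimate design, that the plan openly says of Group 2 that "after the procedure, the patient was prescribed oral dexamethasone", and that a control may be active. On that view this is only a matter of labels. Several parts of the reply stand, and they rule out stronger readings.

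- A reader might infer that the title claims an effect of each treatment against none. It does not say so; a head-to-head comparison is an ordinary reading of it.
- A reader might infer that Group 2 is named as the control. The text never maps the labels to Groups 1 and 2. That is an inference from Group 2 having no biomaterial. If the labels were reversed, the control side would still be actively treated.
- A reader might infer that the two misreadings follow from the plan. They are risks; the plan states no conclusion rule and no results.
- A reader might infer that no between-side test was made. That is not established. The signed-rank test is a paired test and the sides are paired within patients, so the word intra-group could have been used loosely. Dunn is also named in connection with a difference between groups. However, Dunn is a multiple-comparison procedure and there are only two paired sides, so it does not supply the missing comparison.
- A near-certain false signal from intra-group tests holds only for recovery near 1 SD, which is an assumption; the table shows how far it falls for smaller values.

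The reply does not dispose of the main point. Relabelling alone would be wording. Deciding which contrast carries the treatment-effect conclusion changes what the trial can claim.

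**Conclusion.** The concern holds in limited form. The design is not invalid and needs no untreated arm, but it can answer only one treatment question: A-PRF against dexamethasone. The plan does not state that question, calls one of two treated sides a control, and names its signed-rank test only for intra-group comparisons. If those are tests over time, they cannot separate treatment from healing or from the common background drugs. With no treatment effect they would be significant with probability about 0.36 to above 0.99 for assumed recovery of 0.3 to 1 SD.

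The estimability result follows from the allocation of treatments and needs no numerical assumption. The probabilities rest on n = 30, a two-sided 5% level, normal changes and a paired t-test. That A-PRF minus dexamethasone is itself estimable rests on the order of the sides having been randomised, which the plan leaves unsettled.

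**What to change.** 1. State the objective as the within-patient comparison of A-PRF with dexamethasone, and call the dexamethasone side an active comparator.
2. For each outcome and time already planned (VAS, facial measurements, mouth opening), make the paired between-side difference the treatment-effect result. Test it with a paired t-test or Wilcoxon signed-rank test and report it with its 95% CI. Use change from the preoperative value for facial measurements and mouth opening; no preoperative VAS is planned, so VAS is compared directly.
3. Label intra-group changes over time as descriptive recovery curves.
4. State that neither treatment is estimated against no treatment, and that p≥0.05 will not be reported as equal effect or as no effect of A-PRF.
5. Reconcile the two statements on the order of extractions and report which order each patient had. If Group 2 was always second, say that the contrast is confounded with period.

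These changes use data already planned, with no added patients, visits or treatments. The cost is some redrafting and a narrower claim. They do not settle which of the many outcome-by-time differences is primary; that remains a separate decision.

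### Operation order is called random, but its generation and the count per order are not stated, and no named analysis accounts for first versus second operation

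*Combined protocol and SAP*

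**What the plan says.** The Study Protocol section gives the size ("This study was conducted on 30 patients") and the within-patient design: "The tooth extraction on one side of each patient constituted a study group and the other tooth extraction constituted the control group". On timing it says: "The patients were formed into Group 2 so that the other tooth would be extracted 5 weeks later". Surgical Technique and Application says the teeth were extracted "after determining which tooth would be extracted first and which group it would be included in a random manner". No randomisation method, blocking or number of patients per order is given.

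Statistical Analyses lists descriptive summaries, a normality check, one paired test and Dunn's procedure. The paired test is introduced as follows: "Wilcoxon Signed Ranks Test was used in intra-group comparisons of parameters that did not show normal distribution". No term, stratum or sensitivity analysis refers to order, period or sequence. The test for A-PRF versus dexamethasone is not clearly named.

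**The concern.** With two operations 5 weeks apart, the trial is in effect a two-period crossover. Pain is scored by the patient on a 0 to 10 scale and extra analgesic use is recorded by the patient. No masking is described, and one procedure involves a blood draw and a socket filling while the other involves a tablet prescription. A patient who has already been through one extraction may score the second differently, whichever treatment is given.

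If so, each within-patient treatment difference contains the period effect, with a sign that depends on the order. A paired test that pools these differences without regard to order has two weaknesses. Part of the period effect passes into the estimate whenever the orders are unequal in number. The period effect also adds to the variance even when they are equal. Both can be removed using each patient's order, which the trial should hold.

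**Working it through.** **Inputs.** From the documents: 30 patients, both treatments in each patient, 5 weeks between operations, significance level 0.05. The plan gives no power, SD, effect size or period effect, so there is no figure of its own to reproduce. Assumed here: independent 50:50 draws of order, a two-sided test, and a constant additive period effect.

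**Shift in the estimate.** Let τ be the A-PRF minus dexamethasone effect and π the first-minus-second operation effect. The A-PRF minus dexamethasone difference has expectation τ + π in A-PRF-first patients and τ − π in dexamethasone-first patients. With n₁ and n₂ patients in these orders, the pooled mean has expectation

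τ + π (n₁ − n₂)/30.

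Under 50:50 draws n₁ − n₂ averages zero, so the estimate is unbiased over repeated randomisations. For the realised split (binomial, n = 30, p = 0.5):

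| Split | Probability of this or worse | Share of π passed on | Shift if π = 1 VAS point |
|---|---|---|---|
| 17:13 | 0.585 | 4/30 = 13% | 0.13 |
| 18:12 | 0.362 | 6/30 = 20% | 0.20 |
| 19:11 | 0.200 | 8/30 = 27% | 0.27 |
| 20:10 | 0.099 | 10/30 = 33% | 0.33 |

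Exactly 15:15 has probability 0.144. The mean absolute share is also 0.144. A split of 17:13 or closer has probability 1 − 0.362 = 0.638, so in about 64% of draws the share is 13% or less. For π = 0.5 the shifts at 18:12 and 20:10 are 0.10 and 0.17 points; for π = 2 they are 0.40 and 0.67.

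**Extra variance at 15:15.** If σ is the SD of the differences within an order group, the pooled differences have variance σ² + π², and the standard error is inflated by √(1 + (π/σ)²):

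- π = 1, with σ = 1.5, 2, 2.5: 20%, 12%, 8% wider.
- π = 0.5, with the same σ: 5%, 3%, 2% wider.

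**Error rates and power.** A simulation used 20,000 runs per setting, normal differences and a treatment effect of 0.53 SD for power. It compared the signed-rank test without order against a t-test of the treatment effect stratified by order.

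- Simple randomisation, no period effect: power 0.78 unadjusted, 0.79 adjusted. The choice of test alone therefore makes almost no difference.
- Simple randomisation, π = 0.5 SD: type I error about 0.05 for both; power 0.68 unadjusted, 0.79 adjusted.
- Simple randomisation, π = 1 SD: power 0.47 unadjusted, 0.79 adjusted.
- Realised 18:12: unadjusted type I error 0.045 to 0.056 across the period effects tried.
- Realised 20:10, π = 0.5 SD: unadjusted type I error 0.100, adjusted 0.053.
- Forced 15:15, π = 0.5 SD: unadjusted type I error 0.027 and power 0.70, against 0.049 and about 0.80 adjusted.

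Equal numbers per order therefore remove the shift but not the loss of power. Adjustment deals with both.

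**The case against.** The strongest reply has five parts.

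- **The analysis criticised is not clearly the planned one.** The signed-rank test is assigned to intra-group comparisons, which may mean change over time within a group. This stands. The supportable statement is conditional: if that test was used for A-PRF versus dexamethasone, it ignores order. On any reading, no named method supplies a period term.
- **Silence is not imbalance.** A reader might infer that the orders were left unbalanced. The text neither describes nor excludes blocking or a 15:15 list. What can be said is that the method and the counts are not stated.
- **Random order prevents systematic bias.** A reader might infer a biased treatment effect. Under random order the estimate is unbiased on average and overall type I error holds. What remains is a chance shift conditional on the realised split, plus lost power.
- **Typical shifts are modest, and the period effect is assumed.** Both stand. The documents give neither its size nor its direction, and the argument is most natural for self-scored pain. Swelling and mouth opening are measured, with a preoperative value, and nothing in the documents points to a period effect for them.
- **The text is in the past tense.** A restricted order list is probably no longer possible. Reporting the counts and adjusting the analysis still are.

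A stronger inference is also tempting: that dexamethasone always came second, because Group 2 is described as formed "so that the other tooth would be extracted 5 weeks later". Period and treatment would then be completely confounded. The documents do not establish this, because the random-order statement contradicts it; the two passages must be reconciled.

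**Conclusion.** The point holds as an unreported order and a missing adjustment, not as a demonstrated bias. If order was random, the cost is a chance shift averaging about 14% of the period effect in absolute size (33% at 20:10), together with reduced power. The power figures of 0.68 against 0.79 rest on an assumed period effect of 0.5 SD and treatment effect of 0.53 SD. The standard-error inflation of 2% to 20% rests on assumed period effects of 0.5 to 1 VAS point and SDs of 1.5 to 2.5. With no period effect there is no harm. Because the adjustment is nearly free, the change is worth making without knowing how large the effect is. It is available only if both orders occurred, and it assumes the treatment effect is the same at the first and second operation.

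**What to change.** 1. Reconcile the Study Protocol wording on Group 2 with the random-order statement. State how the order was generated and report the number of patients in each order.
2. If both orders occurred, name a period-adjusted analysis for A-PRF versus dexamethasone. One option takes each patient's first-minus-second operation difference, which has expectation π + τ in A-PRF-first and π − τ in dexamethasone-first patients. Compare the two order groups by a rank-sum test and halve the Hodges-Lehmann estimate, since the groups differ by 2τ. The other option is a mixed model with treatment and period as fixed effects and patient as a random effect. Report the period estimate beside the treatment estimate.
3. If only one order occurred, neither analysis can be used. State that treatment and period cannot be separated.

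The cost is one variable (order), a few lines in Statistical Analyses and one degree of freedom. If there is no period effect and the split is uneven, some power is given up: at 20:10 in the simulation, 0.755 adjusted against 0.786 unadjusted. No new data are needed.

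### Pain is scored at 13 times during and after the 3-day dexamethasone course, but the plan has no summary over time and no test of whether the treatment difference changes; a cheap addition would supply both.

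*Combined protocol and SAP*

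**What the plan says.** Under Study Protocol, A-PRF is placed once in the socket on one side. After the other extraction, dexamethasone is prescribed "with the statement that it would be used for 3 days". The design is paired: "This study was conducted on 30 patients", each having both extractions.

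Under Surgical Technique and Application, patients score pain from 0 to 10 "at hours 3, 6, 9, 12, and 24 and days 2, 3, 4, 5, 6, 7, 14, and 30".

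The Statistical Analyses section is one paragraph. Apart from descriptive statistics and checks of normality, it states:
- "Wilcoxon Signed Ranks Test was used in intra-group comparisons of parameters that did not show normal distribution";
- "Dunn was used to determine the group causing the difference", without naming the overall test that this step would follow;
- "significance was at the level of p<0.05".

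It names no repeated-measures model, treatment-by-time term, summary over time, key time point or adjustment for the number of readings.

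**The concern.** A signed-rank test uses one pair of values per patient, and the plan can be read in two ways. If the pair is A-PRF against dexamethasone at one time, a pattern over time would be inferred from p<0.05 at some readings and not at others. If the pair is two times within one treatment, it would be inferred from one treatment reaching p<0.05 and the other not. Neither compares the treatment difference at one time with the treatment difference at another. One significant and one non-significant result can arise from the same true difference.

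A material placed once is being compared with a drug taken for 3 days, so readers will naturally ask whether any difference is early, late or lasting. The plan has no valid way to answer. It could support an early or late advantage that is only noise, or overlook a real change. Adjusting the p-values for multiple testing would not help, because comparing adjusted p-values across times is still not a test of change.

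**Working it through.** The plan gives no effect size, SD, correlation or power figure, so there is nothing of its own to reproduce.

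**Inputs from the documents.** 30 pairs; p<0.05 (two-sided assumed); 5 hourly + 8 daily = 13 readings. Counting day 3 as in-course (a convention, since the plan does not define it), 7 readings fall in the course (hours 3, 6, 9, 12, 24; days 2, 3) and 6 after it (days 4, 5, 6, 7, 14, 30). Eleven fall by day 7.

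**Assumed inputs.** Constant true difference of 1 or 2 points; SD of the paired difference 2 to 3; correlation of the differences between times 0.3 to 0.7.

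**Step 1: mixed verdicts when nothing changes.** Simulated 30-pair trials, a paired t-test at each of the 11 readings to day 7 (standing in for the signed-rank test), true difference constant:

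| True difference | SD, correlation | Day 2 and day 7 verdicts differ | Mixed verdicts over 11 readings |
|---|---|---|---|
| 1 point | 2.5, 0.5 | 33 to 35% | 83 to 84% |
| 1 point | 2 to 3, 0.3 to 0.7 | 20 to 41% | about 55 to 95% |
| 2 points | 2.5, 0.5 | 2% | about 8% |
| 2 points | 2.5, other correlations | – | about 5 to 11% |

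A separate run used actual signed-rank tests on all 13 readings at correlation 0.5. Mixed verdicts occurred in 84%, 88%, 77%, 53% and 11% of trials for standardised differences of 0.3, 0.4, 0.5, 0.6 and 0.8. A single contrast of the two periods rejected in 4.3 to 5.6% of trials in every scenario.

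**Step 2: gain from averaging the in-course readings.** For a 1-point difference at SD 2.5, one reading has power of about 56% (noncentral t, n = 30). For an unweighted mean of 7 readings with equal correlation r, the SD is 2.5 × √((1 + 6r)/7):
- r = 0.3: 2.5 × 0.632 = 1.58, power 92%;
- r = 0.5: 2.5 × 0.756 = 1.89, power 80%;
- r = 0.7: 2.5 × 0.862 = 2.15, power about 69%.

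With serial correlation included, the range is about 66 to 92%.

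**Step 3: why to weight by time.** Five of the 7 in-course readings fall in the first 24 hours, so an unweighted mean gives that day 5/7 = 71% of the weight. Trapezoid weights from hour 3 to hour 72 are 1.5, 3, 3, 7.5, 18, 24 and 12, which sum to 69. The share of readings up to hour 24 becomes 33/69 = 48%. The cost in precision is small. The squared weights sum to 1120.5/4761 = 0.235, so at r = 0.5 the SD is 2.5 × √(0.5 + 0.5 × 0.235) = 1.97 instead of 1.89, and power is about 77%.

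**Step 4: what the contrast of windows can detect.** True fall from 1 point to 0, SD 2.5, unweighted windows. If correlation decays with separation in time, power is about 58 to 82% and the 95% half-width about 0.7 to 0.9 point. Equal correlation between all times gives a more favourable answer (98% or more, half-width 0.3 to 0.5), but it requires hour 3 to correlate with day 7 as strongly as with hour 6.

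**Step 5: what the contrast means.** Let pain fall from 4–5 to 0.5 by day 7 with a constant 25% relative effect and no effect of stopping the tablets (all assumed). The contrast then reports a change in 41 to 95% of simulated trials, because absolute differences shrink as pain approaches 0.

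**The case against.** The strongest reply is that the documents state no time-course objective and plan no early or late claim, so the harm arises only if the authors draw one. That stands. The means and medians that the plan does provide can describe a time course without any significance verdict. It is also true that a more basic matter comes first: the signed-rank test is described only for comparisons within groups, so even the single-time comparison of A-PRF with dexamethasone is not clearly specified.

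Three stronger readings are tempting and not supported:
- A reader might infer that separate p-values will usually produce a false pattern. That depends on effect size, SD and correlation, none of which the documents give. With a large constant effect, mixed verdicts become uncommon.
- A reader might infer that a contrast of the two windows shows what happens when the tablets stop. It does not: resolving pain alone can produce a change in the absolute difference, and the in-course window is dominated by early readings unless weighted.
- A reader might infer that the contrast is almost certain to detect a lost effect. That holds only under equal correlation between all times.

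What survives is that the plan collects a dense pain series and has neither a summary of it nor a valid test for a statement about early against late.

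**Conclusion.** The point holds as a low-cost improvement and not as a defect that undermines the trial. The number of readings, the 3-day course and the absence of any time summary or test of change are plain from the text. That comparing p-values does not test a change needs no assumption. How often it would mislead does: often for a small to moderate constant effect, seldom for a large one. Averaging within a window also raises power over a single reading in the scenarios examined at 1 point and SD 2.5. The contrast is worth having as a check on claims, with moderate power, and should be read only as a change in the absolute difference.

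**What to change.** Add to Statistical Analyses:

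- For each operation, compute a time-weighted mean VAS (area under the curve divided by duration) from hour 3 to day 3 and from day 4 to day 7. State that counting day 3 as in-course is an analysis convention.
- In each window, test the within-patient A-PRF minus dexamethasone difference with the Wilcoxon signed-rank test, and report the estimate and 95% interval.
- As a secondary analysis, test the paired contrast of the two window differences in the same way. Make no claim that the difference is larger early or late unless this contrast supports it, and describe it as a change in the absolute difference, not as an effect of stopping the tablets.
- Treat all single-time results, including days 14 and 30, as descriptive.
- The protocol is written in the past tense. If data have already been seen, label these analyses post hoc.

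The cost is a few sentences and three paired tests on readings already scheduled, plus a rule for missed diary entries, which the area under the curve will need. The downside is that a brief difference confined to one reading is averaged out, and single-time p-values lose confirmatory status.

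### Does asking patients to note only *additional* analgesic use leave the as-needed ibuprofen unrecorded, so that the pain scores cannot be read?

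*Combined protocol and SAP*

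**What the plan says.** Three statements in Surgical Technique and Application bear on the point.

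- The prescription for all patients includes "ibuprofen 600 mg (Brufen 600 mg, 2*1".
- The instruction separates the drugs: "They were asked to use the antibiotic and mouthwash as recommended and to take painkillers when needed".
- The record is described in one sentence: "In order to evaluate the patients' analgesic use, patients were asked to note their additional analgesic use on the forms given to them".

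Pain is scored by the patient on a 0 to 10 VAS "at hours 3, 6, 9, 12, and 24 and days 2, 3, 4, 5, 6, 7, 14, and 30". No pill count or other intake record is described, and the form is not reproduced.

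Statistical Analyses names no individual outcome. It gives descriptive summaries for quantitative and qualitative variables and states that "Wilcoxon Signed Ranks Test was used in intra-group comparisons of parameters that did not show normal distribution".

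The two operations differ in ways a patient would notice. Blood is drawn "Before the operation where the surgical area where A-PRF would be applied was located, 1 tube, 10 cc", and after the other operation "the patient was prescribed oral dexamethasone (Dekort 4 mg tablet, S:3*1 DEVA brand) with the statement that it would be used for 3 days". No sham draw or placebo tablet is described.

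**The concern.** The aim is to evaluate analgesic use, but the form asks for *additional* use, and the text does not say additional to what. Beside a prescription written 2*1, a reader may take it to mean anything beyond the prescribed ibuprofen. The form would then omit the drug whose intake is most likely to rise and fall with pain.

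This would matter because VAS is scored while patients adjust their own analgesia. Similar scores with unequal intake do not mean similar pain control. The split-mouth design balances a patient's general tendency to take tablets, but not a difference in intake that the treatment itself causes. If ibuprofen were left out, equal recorded use would not show equal intake. Statistical Analyses does not say how intake is to be compared between sides or read beside VAS.

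**Working it through.** **1. The two readings.** The plan gives no figure on analgesic intake, so there is nothing to reproduce, and the question turns on the text.

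- *Narrow reading: only drugs beyond the ibuprofen.* This needs a baseline from which additional use is counted. The 2*1 could supply one, if it was a fixed regimen.
- *Broad reading: every painkiller tablet taken.* The instruction contrasts the antibiotic and mouthwash, which follow the prescription, with painkillers, which follow need. The 2*1 is then what was prescribed, and need decides how much is taken. There is no fixed baseline, and *additional* naturally means whatever was taken beyond the drugs used on schedule. The stated aim of the sentence fits this reading and does not fit the narrow one.

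The text does not prove the broad reading, but it supports it at least as well as the narrow one. It does not show that ibuprofen was left out.

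**2. What the narrow reading would cost.** Inputs: 2*1 read as two doses a day; a duration of 3 to 7 days, which is an assumption because none is given.

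- Uncounted doses per operation, at most: 2 × 3 = 6, or 2 × 7 = 14.
- VAS times in that window: hours 3, 6, 9, 12 and 24 give 5. Days 2 and 3 bring this to 5 + 2 = 7 of 13 by day 3. Days 2 to 7 bring it to 5 + 6 = 11 of 13 by day 7.
- Suppose the true mean difference between sides were 3 doses (assumed), and a fraction q of patients left ibuprofen out on both sides and had the same mean difference as the rest. The recorded difference is 3 × (1 − q), which is 3, 2, 1.5 and 0 for q = 0, 1/3, 1/2 and 1.

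The last line only restates that unrecorded doses are not recorded. Neither the 3 doses nor q comes from the documents, so it does not measure a fault in this trial.

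**3. Precision of a paired comparison in 30 patients.**

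- Half-width of the 95% CI for a mean difference: t(0.975, 29 df)/√30 = 2.045/5.477 = 0.373 SD of the paired differences.
- Exact McNemar test, if the forms hold only yes or no and all discordant patients go one way: 2 × 0.5^6 = 0.031 with 6 patients; 2 × 0.5^5 = 0.0625 with 5.

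A non-significant intake test would therefore not establish equal intake. But these figures hold for any outcome in 30 pairs and would be the same if *additional* had been defined perfectly.

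**4. Effect on VAS.** Pain under as-needed analgesia is a legitimate target. If intake follows pain by the same rule on both sides, the VAS difference shrinks toward zero relative to pain without painkillers. To create or exaggerate a difference, intake must differ between sides for some other reason, and the documents show no such imbalance. Patients could tell the operations apart, but that this changed their tablet use is conjecture.

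**5. The analysis.** The plan says analgesic use is to be evaluated, and its descriptive methods cover both counts and yes/no data. Each patient contributes both sides, so the signed-rank test it names is the natural paired test for counts. For yes/no data it names no test; McNemar's is the standard choice. That the test is described as intra-group is a looseness affecting VAS, edema and trismus equally, and is not particular to analgesic use.

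**The case for a change.** The strongest case for a change is that the three statements do not give the record one settled meaning, nothing else in the document supplies it, and the remedy is cheap. One sentence would define *additional*, one would state that VAS measures pain under as-needed analgesia, and one paired comparison would use data already collected. Unblinded patients might also take tablets differently after an operation that came with a steroid.

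Much of this stands. The word is undefined, the form cannot be inspected, and VAS under patient-controlled analgesia is best read beside intake. But the first two sentences only write down a definition and a target, and the third applies ordinary paired methods to a variable the plan already sets out to evaluate. None corrects a step that would give a wrong result if followed.

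A stricter rule, barring any conclusion from VAS when intake differs, would do harm: lower pain with lower intake on the same side strengthens the conclusion. Such a rule would also need a criterion for when intake differs, and the material offers none.

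**Conclusion.** No change to the plan is called for. This is missing detail that an analyst fills sensibly: look at the completed forms, state whether ibuprofen was counted, and report recorded use for each side, with the paired difference, beside VAS. If the forms do not show it, the record is reported descriptively with that limitation. The protocol is written as an account of a study already conducted, so redefining the word now could not recover tablets that were not noted, and if they were noted nothing is lost.

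The size of any bias in VAS cannot be derived from the documents. The only bound available is at most 6 to 14 uncounted ibuprofen doses per operation. It rests on the narrow reading of *additional*, on two doses a day and on an assumed 3 to 7 days of use.

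The conclusion rests on the broad reading being at least as natural as the narrow one and on the absence of any documented imbalance in intake. It does not rest on the order of the operations. Completed forms that plainly excluded ibuprofen would limit how the results are read, but would still not be mended by rewording the plan.
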